2.2 Secondary Objectives

1. Evaluate the efficacy and safety of treatment with high-titer versus low-titer anti-influenza immune plasma as an addition to standard care, using the following parameters:

- The ordinal primary outcome assessed at Days 1, 2, 3, 14, and 28
- Duration of initial hospitalization
- 28-day mortality
- In-hospital mortality during initial hospitalization
- Composite of mortality and hospitalization at Days 7, 14, and 28
- Change from baseline to Day 3 and Day 7 in NEW/PEW score
- Duration of supplemental oxygen use among those requiring oxygen at randomization
- Incidence of new oxygen use during the study
- Duration of ICU stay among those requiring ICU admission at randomization
- Incidence of new ICU admission during the study
- Duration of mechanical ventilation use among those requiring mechanical ventilation at randomization
- Incidence of new mechanical ventilation use during the study
- Duration and severity of ARDS among those meeting the definition of ARDS at randomization
- Incidence and severity of new ARDS during the study
- Duration of ECMO use among those requiring ECMO at randomization
- Incidence of new ECMO use during the study
- Change from baseline to Day 3 and Day 7 SOFA score for age \geq 18 years, and PELOD score for age $<$ 18 years
- Disposition (home, rehabilitation, chronic nursing facility, initial hospitalization ongoing at 28 days, died in hospital) following the initial hospitalization

- Percent of subjects with influenza virus detectable in OP sample at Day 3

2. Compare the plasma and control groups for HAI titers at Days 1, 3, and 7.

3. Evaluate the safety of high titer anti-influenza plasma as compared to low titer plasma as assessed by:

- Cumulative incidence of grade 3 and grade 4 adverse events (AEs)
- Cumulative incidence of serious adverse events (SAEs)

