7.3.6 ARDS

The incidence of ARDS will be assessed at each study day using the revised Berlin definition of ARDS. [22]

Table 10: Berlin Criteria for ARDS

| Acute Respiratory Distress Syndrome | |
|-------------------------------------|---|
| Timing | Within 1 week of a known clinical insult or new or worsening respiratory symptoms |
| Chest imaging ^a | Bilateral opacities—not fully explained by effusions, lobar/lung collapse, or nodules |
| Origin of edema | Respiratory failure not fully explained by cardiac failure or fluid overload Need objective assessment (eg, echocardiography) to exclude hydrostatic edema if no risk factor present |
| Oxygenation ^b | |
| Mild | 200 mm Hg < $\text{PaO}_2/\text{FiO}_2 \leq 300$ mm Hg with PEEP or CPAP ≥ 5 cm H ₂ O ^c |
| Moderate | 100 mm Hg < $\text{PaO}_2/\text{FiO}_2 \leq 200$ mm Hg with PEEP ≥ 5 cm H ₂ O |
| Severe | $\text{PaO}_2/\text{FiO}_2 \leq 100$ mm Hg with PEEP ≥ 5 cm H ₂ O |

Abbreviations: CPAP, continuous positive airway pressure; FiO_2 , fraction of inspired oxygen; PaO_2 , partial pressure of arterial oxygen; PEEP, positive end-expiratory pressure.

^aChest radiograph or computed tomography scan.

^bIf altitude is higher than 1000 m, the correction factor should be calculated as follows: [$\text{PaO}_2/\text{FiO}_2 \times (\text{barometric pressure}/760)$].

^cThis may be delivered noninvasively in the mild acute respiratory distress syndrome group.

If PaO_2 is not available, the Manual of Operations (MOP) provides instructions for estimating the $\text{PaO}_2/\text{FiO}_2$ ratio from the FiO_2 and SpO_2 .

The oxygenation assessment should be within 4 hours of the assessment of ARDS. If there is no chest imaging on the day of assessment, the most recent imaging may be used. Subjects meeting all criteria meet criteria for ARDS. Severity should be graded based on the oxygenation in the above table.

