12.4.2 Secondary Endpoints

- Ordinal outcome assessed at Days 1, 2, 3, 7, 14, and 28
- Date of hospital admission and discharge
- Date and cause of death (if applicable)
- NEW/PEW score at Day 0, 3, and 7
- Date/time of supplemental oxygen initiation and discontinuation (if applicable)
- Date/time of ICU admission and discharge (if applicable)
- Date/time of mechanical ventilation initiation and discontinuation (if applicable)
- Date/time of meeting ARDS criteria, date of resolution, and severity (if applicable)
- Date/time of ECMO initiation and discontinuation (if applicable)
- SOFA score for age \geq 18 years and PELOD score for age $<$ 18 years on Days 0, 3, and 7
- Disposition (home, rehabilitation, chronic nursing facility) following the initial hospitalization
- Quantitative PCR for influenza in oral swab on Day 0 and 3.
- Grade 3 and 4 adverse events
- SAEs
- Safety laboratory tests will be collected on Days 0, 1, 3, and 7
- CBC with differential white cell count (to include neutrophil and lymphocyte percentages), hemoglobin, hematocrit, and platelets
- Blood chemistries (creatinine, glucose, total protein, ALT/GPT, AST/GOT, total bilirubin)
 - Hemagglutination Inhibition (HAI) titer Days 0, 1, 3, 7
 - Grade 3 and grade 4 adverse events (AEs)
 - Serious adverse events (SAEs)

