## 6. Baseline characteristics (mITT population)

Baseline characteristics are those recorded as Day 0; if values are missing but are available from screening assessments, then these will be used instead. Tables in this section will show number (%) for categorical variables, and median, 25th and 75th percentiles, min and max for the ordinal/continuous variables; number with missing values. No statistical comparison will be undertaken between randomized arms (instead, the impact of any imbalance may be evaluated in adjusted analyses—see efficacy analyses section).

- a. Table: Number randomized: overall and by month/influenza season (generally November – March, but for grouping will be August – July). Dates of first and last randomizations.
- b. Table: Number randomized by site.
- c. Table of demographic characteristics: Age at randomization and associated age group (adult versus child, with children classified as <2 years, ≥2 to <8 years, and ≥8 to <18 years); sex;

pregnancy status; self-reported NIH race/ethnicity (major category race, minor category ethnicity).

- d. Table of body mass index (BMI) and BMI group (adults only, using standard U.S. categories for underweight, etc.).
- e. Table of influenza disease status: Influenza vaccination in the current season; days from onset of influenza symptoms to randomization; influenza antivirals taken through to randomization (number (%)) for each specific drug or combination of drugs, and number (%) taking any antivirals); influenza status by site testing (negative versus positive, type of testing), influenza status from central lab from Day 0 (negative versus positive) and subtype from central laboratory testing; viral shedding in OP sample by qPCR at central laboratory testing.
- f. Table of days hospitalized prior to randomization
- g. Table of chronic medical conditions and allergies (defined as starting >30 days prior to randomization), by MedDRA SOC and PT.
- h. Table of vital signs, including SaO2.
- i. Table of clinical status: Study 6-point ordinal scale; measures of clinical support (hospitalization, oxygen requirement, mechanical ventilator requirement, ICU requirement, ECMO requirement), ARDS (yes/no, and by severity)
- j. Table of respiratory status: PaO2/ FiO2 Ratio, SpO2/ FiO2 Ratio [excluding those on ECMO as these criteria are erroneous in this population].

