## **10.4 Secondary endpoints: Hospitalization, intensive care/support and ARDS**

The protocol specifies the following secondary endpoints:

- Duration of initial hospitalization
- Duration of all hospitalizations
- Duration of admission to an ICU among those in an ICU at randomization
- Incidence of new ICU admission among those not in an ICU at randomization
- Duration of supplemental oxygen use among those requiring oxygen at randomization
- Incidence of supplemental oxygen use among those not requiring oxygen at randomization
- Duration of mechanical ventilation use among those requiring mechanical ventilation at randomization
- Incidence of new mechanical ventilation use among those not requiring mechanical ventilation at randomization

- Duration of ECMO use among those on ECMO at randomization
- Incidence of new ECMO use among those not on ECMO at randomization
- Duration of ARDS among those with ARDS at randomization
- Incidence of new ARDS among those not having ARDS at randomization

Notes:

- i. Each of these measures will be evaluated through to the Day 28 visit and so will reflect the use of interventions (or of ARDS) during the study follow-up period.
- ii. Deaths and losses to follow-up may affect the interpretation of the results for these endpoints (e.g. deaths, losses to follow-up). Sensitivity analyses may be undertaken to assess how the interpretation of formal analyses might be affected by these issues.

- a. Table showing durations of interventions: n (will be overall sample size for hospitalizations, and number receiving intervention at randomization for other interventions and ARDS), median, 25th and 75th percentiles and min, max. Difference in medians between treatments, p-value from Wilcoxon's test and associated 95% CI for difference.
- b. Table showing incident use of intervention (or new development of ARDS): n (will be number not receiving intervention or not having ARDS at randomization), number (%) with incident use of intervention (or new development of ARDS), difference in %'s between treatments, and odds ratio comparing treatments with p-value and associated 95% CI from exact logistic regression.

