## **10.5 Secondary endpoints: NEW/SOFA Scores in adults, and PEW/PELOD Scores in children**

The NEW and SOFA Scores are evaluated in subjects of age  $\geq 18$  years, and the PEW and PELOD Scores are evaluated in subjects of age  $< 18$  years. The Scores are evaluated at Day 0, and Days 3 and 7.

Notes:

- If a subject has a missing Score at Day 0, the subject will be excluded from the analysis. If a subject has a missing Score at Day 3 (or at Day 7) for reason other than death, then the last available Score will be used instead.
- If a subject was on ECMO on Day 0, the subject will be excluded from the analysis as these scores are affected by the ECMO intervention.
- For a subject who dies without having a Score obtained at Day 3 (or at Day 7), then the Score and change in Score will be assumed to be (ie ranked) worse than any Score and change in Score for a subject who has a Score at Day 3 (or at Day 7).
- For a subject who starts ECMO during follow-up, then the Score and change in Score on those days when on ECMO will be assumed to be (ie ranked) worse than any Score and change in Score for a subject who has Score on that day (but ranked better than a subject who died before that day).

- a. Table: Completeness of evaluations for Score showing number (%) at each visit who:

- i. have all of the evaluations necessary to calculate the Score
- ii. have some but not all evaluations necessary to calculate the Score
- iii. died prior to the visit
- iv. were lost to follow-up prior to the visit
- v. were in follow-up but on ECMO
- vi. were in follow-up but have missing values for all of the evaluations necessary to calculate the Score.

b. Table: median, 25th and 75th percentiles, min and max Score at each of Days 0, 3 and 7, showing also number missing.

c. Table: median, 25th and 75th percentiles, min and max of change in Score at each of Days 3 and 7, showing also number missing. At each of Days 3 and 7: difference in medians between treatments, p-value from Wilcoxon's test and associated 95% CI for difference. Wei-Johnson Test will be used to provide a comparison between treatments combining over Days 3 and 7.

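### SAP 10.4 has no rule for days on ECMO in the ARDS duration and new-ARDS endpoints, although the SAP calls the underlying oxygenation criteria erroneous on ECMO

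*SAP*

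**What the plan says.** **Definition.** Protocol 7.3.6 states: "The incidence of ARDS will be assessed at each study day using the revised Berlin definition of ARDS". Its Table 10 requires PaO2/FiO2 of 300 mm Hg or less with PEEP or CPAP of at least 5 cm H2O, together with timing, imaging and oedema-origin criteria. The ratio may be estimated from SpO2 when PaO2 is missing. The section adds: "Subjects meeting all criteria meet criteria for ARDS. Severity should be graded based on the oxygenation in the above table". It does not mention ECMO.

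**Endpoints.** SAP 10.4 analyses "Duration of ARDS among those with ARDS at randomization" by Wilcoxon's test and "Incidence of new ARDS among those not having ARDS at randomization" by exact logistic regression, both through the Day 28 visit. Its notes on interpretation name deaths and losses to follow-up only.

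**ECMO elsewhere in the SAP.** Section 6, item j, presents PaO2/FiO2 and SpO2/FiO2 at baseline "excluding those on ECMO as these criteria are erroneous in this population". Item i, directly before it, tabulates ARDS status and severity with no such exclusion. In SAP 10.5 a subject on ECMO on Day 0 is "excluded from the analysis as these scores are affected by the ECMO intervention". Later ECMO days are ranked worse than any observed score and better than death.

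**Severity.** Protocol 2.2 lists "Duration and severity of ARDS among those meeting the definition of ARDS at randomization" and also pairs severity with the incidence of new ARDS. The SAP's protocol summary repeats both. The list in SAP 10.4 carries neither severity component.

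**The concern.** The SAP declares a measurement invalid on ECMO and protects the early-warning and organ-dysfunction scores from it. It then uses the same measurement, unprotected, to decide whether ARDS is present. ECMO supplies oxygen outside the lung, so the ratio may improve while the lung does not.

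If that happens, escalation to ECMO could end an ARDS episode in the data, and one of the sickest subjects could rank among the shortest durations. SAP 10.5 ranks the same subject next to death, so two sections of one report could point in opposite directions. Were high-titer plasma to prevent ECMO, some of that benefit could appear as longer ARDS in the high-titer arm.

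The severity omission is a separate matter. The baseline table is the only ARDS severity output in the SAP, so severity after randomization would never be compared between arms.

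**Working it through.** The plan states no power or sample-size figure for the ARDS endpoints, so there is nothing to reproduce. The check traces the rules, with simple arithmetic for scale.

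**1. Can the ratio alone change ARDS status?** Yes. All Table 10 criteria must hold, so a ratio above 300, or PEEP/CPAP below 5, is enough for ARDS to be recorded as absent. Protocol 12.4.2 collects a date of resolution, but neither document defines resolution.

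**2. Which way could it go on ECMO?** These values are illustrative and do not come from the documents:
- PaO2 90 on FiO2 0.28: 90 / 0.28 = 321, above 300, so the criteria are not met.
- PaO2 80 on FiO2 0.30: 80 / 0.30 = 267, at or below 300, so mild ARDS is still met if the other criteria hold.

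False resolution is therefore possible but not certain.

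**3. Paths through SAP 10.4 as written**
- *ARDS at randomization, then ECMO.* Suppose ECMO runs from Day 2 to Day 20 with unchanged lung disease. If the criteria are unmet on ECMO, the duration could be about 2 days instead of at least 20. If the criteria are met again off ECMO, the episode reopens, and the SAP does not say how to count it.
- *On ECMO at randomization, recorded without ARDS.* The subject enters the new-ARDS denominator. Meeting the criteria after ECMO stops counts as an event, although coming off ECMO may mark improvement.
- *No ARDS at randomization, ECMO started before any assessment records ARDS.* ARDS may be missed on ECMO, or first counted after it.
- *ARDS at randomization, then on and off ECMO.* This subject is outside the incidence denominator and cannot become a new-ARDS event.

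**4. Scale**
- Sample size is 150, randomized 2:1 (Protocol 3.3). Baseline ARDS was 38% in the earlier plasma trial (Protocol 1.2.2.4).
- 0.38 x 150 = 57 subjects with ARDS, about 57 x 2/3 = 38 high-titer and 57 x 1/3 = 19 low-titer. This is approximate, because the earlier trial also enrolled influenza B and had different entry criteria.
- The documents give no ECMO rate. At an assumed 2-8%: 0.02 x 150 = 3 and 0.08 x 150 = 12 subjects on ECMO at some time. These are the subjects exposed to the gap. They need not all be among the 57.

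**5. Severity.** Of the protocol's four ARDS components (duration, incidence, and severity for each), SAP 10.4 keeps two. Section 6, item i, covers severity at baseline only.

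**The case against.** The strongest reply is that the SAP calls the ratios erroneous on ECMO without saying which way they err. The second example in the working shows that a subject on ECMO can still meet the criteria. That stands: the plan permits mis-scoring but does not guarantee it.

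Other replies have some force. New ECMO use and ECMO duration are analysed in the same section, so an effect on ECMO would be seen directly. The primary ordinal scale does not use PaO2/FiO2. The Manual of Operations, which Protocol 7.3.6 cites for estimating the ratio, was not available and might contain an ECMO rule. These points limit the harm. They do not supply the rule, and an endpoint derivation belongs in the SAP.

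A reader might infer that the sickest subjects are scored in the wrong direction on both endpoints, or that coming off ECMO generally counts as new ARDS. The documents support neither. The first needs a direction of error that they do not give. The second applies mainly to subjects on ECMO at randomization who were recorded without ARDS. Nor is every subject on ECMO mis-scored.

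**Conclusion.** The gap holds on the text and is an inconsistency within the SAP. Section 6, item j, and section 10.5 treat these measurements as unreliable on ECMO, while 10.4 and item i of section 6 use the same ratio with no rule. Followed as written, the plan can date ARDS as resolved during ECMO. It can also create a new-ARDS event in a subject who was on ECMO at randomization.

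The size is uncertain. Under an assumed 2-8% ECMO use, 3-12 of 150 subjects are exposed; how many would be mis-scored cannot be derived. Only secondary endpoints are touched. The change should be made, but it does not threaten the primary analysis.

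The missing post-baseline severity comparison is also correct on the text and does not depend on the ECMO question.

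**What to change.** In SAP 10.4, with a matching note at section 6, item i:
- For a subject who has met ARDS, days on ECMO do not count as resolution. ARDS is ongoing until the criteria are unmet off ECMO.
- Subjects on ECMO at randomization are excluded from the new-ARDS denominator, in line with 10.5. A sensitivity analysis counts them as having ARDS at randomization.
- State how to count a subject without ARDS at randomization who starts ECMO before ARDS is recorded. The two rules above do not settle this.

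Separately, restore severity. Compare the worst post-baseline ARDS grade on assessed study days between arms, separately for subjects with and without ARDS at randomization, with ECMO and death ranked as in 10.5. Day 0 is left out so that the pre-treatment grade cannot set the outcome. ARDS is assessed on study days rather than daily, and telephone visits omit it, so the wording should refer to assessed days.

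The cost is SAP text and a derived-variable rule. ECMO dates and ARDS dates and severity are already collected (Protocol 7.3.7 and 12.4.2). One small downside is that a rare subject who has met ARDS but stays on ECMO for a cardiac reason is counted as having ongoing ARDS. Death during ARDS is not resolved by this change and stays under the existing caveat in 10.4.

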12.3 Statistical Analysis

A detailed statistical analysis plan will be developed before undertaking any comparative analyses of outcomes for the randomized high and low plasma titers. The following provides a brief summary of approach to analysis for the primary endpoint.

As noted above, the primary analysis will use a modified intention-to-treat approach which excludes randomized subjects who do not have an infusion of study plasma started. Statistical inferences will use a two-sided Type 1 error rate of 0.05, and corresponding 95% confidence intervals.

Analysis of the primary endpoint (ordinal outcome of clinical status at Day 7) will use a proportional odds model with an indicator variable for randomized treatment. It is useful to note that the score test of the treatment effect from a proportional odds model is equivalent to a Wilcoxon rank sum test even if the proportional odds assumption does not hold. If there are missing data for the primary endpoint, then sensitivity analyses will be undertaken to evaluate the sensitivity of study conclusions to the handling of the missing data. The proportional odds model will be extended to undertake comparisons of randomized treatments adjusted for variables that might be predictive of the outcome, for example, the ordinal clinical status at baseline. The model will also be extended to evaluate possible differences in the comparison of randomized treatments between subgroups of subjects (treatment by subgroup interaction), including subgroups defined by sex, age (adult/child), race/ethnicity, ordinal clinical status at baseline, NEW score at baseline, and days since onset of influenza symptoms to randomization.

Binary variables such as 28-day mortality, in-hospital mortality, incidence of new ICU admissions, etc., are expected to occur infrequently and will be compared between randomized arms using exact logistic regression. Quantitative variables such as duration of ICU stay and change from baseline in NEW score, etc., are expected to have reasonably skewed distributions and may be subject to censoring (e.g., for subjects in an ICU on Day 28); these will be compared between randomized arms using non-parametric tests (e.g., Wilcoxon's Test adapted, if necessary, to handle censoring).

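### SAP 10.4b puts subjects who die without the event among the non-events, and no analysis that counts those deaths is required

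*SAP*

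**What the plan says.** SAP 10.4 lists five incidence endpoints: new ICU admission, supplemental oxygen, mechanical ventilation, ECMO and ARDS, each among subjects free of it at randomization. Item b gives the denominator as "n (will be number not receiving intervention or not having ARDS at randomization", the numerator as "number (%) with incident use of intervention (or new development of ARDS", and the result as an "odds ratio comparing treatments with p-value and associated 95% CI from exact logistic regression". Note i sets the horizon: "Each of these measures will be evaluated through to the Day 28 visit". Protocol 12.3 agrees on method: binary variables, with new ICU admissions among its examples, "will be compared between randomized arms using exact logistic regression".

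Note ii of SAP 10.4 recognises the issue: "Deaths and losses to follow-up may affect the interpretation of the results for these endpoints". Its remedy is: "Sensitivity analyses may be undertaken to assess how the interpretation of formal analyses might be affected by these issues". No method is named and nothing is required.

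Other parts of the SAP do fix a place for death. In 10.5, a subject who dies without a score has a result that "will be assumed to be (ie ranked) worse than any Score and change in Score" of a subject with one, and a subject on ECMO ranks above a subject who died. Section 10.2b combines death with hospitalization, and 10.3 gives death during the initial hospitalization its own category.

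**The concern.** Death prevents any later ICU admission, ventilation, ECMO or ARDS assessment. With the denominator fixed at randomization and only incident events counted, an early death without the event has the same effect on the odds ratio as a recovery. When deaths differ by arm, the odds ratio mixes less escalation with less time alive to escalate. If high-titer plasma prevents deaths, its extra survivors remain at risk of escalation and its incidence rows look slightly worse. If it causes deaths, those rows look slightly better.

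For ECMO the effective order is the reverse of that in 10.5: a subject who dies without ECMO is placed better than one who receives it. Each row carries its own odds ratio, confidence interval and p-value, and nothing in the table shows how many deaths lie in the non-event cell.

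**Working it through.** **The plan's own figure.** The only sizing figure is for the primary endpoint: 80% power at a proportional odds ratio of 2.50 with 135 subjects (Protocol 12.2). Whitehead's formula is power = Φ(ln OR × √[N × (2/9) × (1 − Σp̄³)/3] − 1.96), where p̄ is the 2:1-weighted mean of the Table 12 columns. It gives 80.7%, and 90.3% at an odds ratio of 2.88. Both reproduce, and this point does not affect them. The documents give no event rates for the incidence endpoints, so those below are assumed.

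**Inputs.** Death proportions (low-titer v high-titer): 10% v 4.3% and 10% v 3.7% from Table 12, and 5/45 = 11.1% v 1/42 = 2.4% from the earlier trial IRC002 (Protocol 1.2.2.4). Event risk if nobody died: 5% to 40%, assumed equal in both arms, so that any difference comes from deaths alone.

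**Case 1: death and event independent.** With constant hazards hE = −ln(1 − e) and hD = −ln(1 − d), item b would report hE/(hE + hD) × [1 − (1 − e)(1 − d)]. For e = 20% and d = 10%: 0.2231/(0.2231 + 0.1054) × (1 − 0.80 × 0.90) = 0.679 × 0.28 = 19.0%. For d = 4.3%: 0.2231/(0.2231 + 0.0440) × 0.2344 = 19.6%.

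| Deaths, low v high | Event risk | Reported, low v high | Difference (points) | Odds ratio, high v low |
|---|---|---|---|---|
| 10% v 4.3% | 5% | 4.75% v 4.89% | 0.14 | 1.03 |
| 10% v 4.3% | 20% | 19.02% v 19.58% | 0.56 | 1.04 |
| 10% v 4.3% | 40% | 38.13% v 39.21% | 1.07 | 1.05 |
| 10% v 3.7% | 20% | 19.02% v 19.64% | 0.62 | 1.04 |
| 11.1% v 2.4% | 5% | 4.72% v 4.94% | 0.22 | 1.05 |
| 11.1% v 2.4% | 40% | 37.92% v 39.56% | 1.64 | 1.07 |

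The arm with more deaths always shows fewer events, by 0.1 to 1.6 points. For the 20% row at 10% v 4.3%, event or death is 28.0% v 23.4%, which favours high-titer.

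**Case 2: deaths pre-empt events.** Suppose 20% in each arm would have had the event, and a fraction f of deaths removes one. Reported proportions are 20% − f × 10% and 20% − f × 4.3%.
- f = 0.5: 15.0% v 17.9%, odds ratio 1.23.
- f = 1: 10.0% v 15.7%, a gap of 5.7 points, odds ratio (0.157/0.843)/(0.10/0.90) = 1.68.

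This ceiling is simply the difference in deaths (10 − 4.3 = 5.7), so it would be 6.3 points at 10% v 3.7% and 8.7 at 11.1% v 2.4%.

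**Size of the at-risk sets.** Protocol 1.2.2.4 reports that at baseline 58% of IRC002 subjects were in ICU, 82% on oxygen, 43% ventilated and 38% with ARDS. Applying these shares to 45 low-titer and 90 high-titer subjects (an assumption):
- no ICU (42%): 19 v 38
- no oxygen (18%): 8 v 16
- no ventilation (57%): 26 v 51
- no ARDS (62%): 28 v 56

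Even at the full 10%, low-titer deaths in these sets would number about 1.9, 0.8, 2.6 and 2.8. The ventilation set contains some very sick subjects, since at least 58 − 43 = 15% were in ICU but not ventilated. For scale, with 26 v 51 subjects and 20% events in each arm, the standard error of the log odds ratio is √[1/(26 × 0.16) + 1/(51 × 0.16)] = 0.60. The 95% limits are then a factor of exp(1.96 × 0.60), about 3.3, either side.

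**Can the direction differ?** With wholly assumed counts (low: 4 events and 5 deaths without the event among 45; high: 10 and 3 among 90), events alone give 8.9% v 11.1%, odds ratio 1.28. Event or death gives 20.0% v 14.4%, odds ratio 0.68. Neither is near significance (Fisher p = 0.77 and 0.46). This shows only that the two summaries can point in opposite directions.

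**The case against.** **The SAP never says that deaths are event-free.** True: it follows from item b's denominator and numerator. The general rule in SAP section 1, restricting analyses to subjects with non-missing data, could be read as dropping these subjects, although item b's explicit denominator points the other way. Dropping them would not count the deaths against an arm either. In the 20% example it gives 19.02/(100 − 8.98) = 20.9% v 19.58/(100 − 3.86) = 20.4%, a small shift the other way. The reading therefore has to be settled.

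**Death is not hidden.** This stands. SAP 8.1 tests in-hospital and Day 28 mortality, 10.2a compares the ordinal scale with death worst at each study day, and 10.2b and 10.3 include death. A reader might infer that a harmful arm could pass as beneficial. Read together, the analyses do not allow that.

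**The size is easily overstated.** This also stands. A reader might multiply Table 12 deaths by a guessed share dying without the intervention: 25% to 50% gives gaps of 1.4 to 2.9 points, and 90% for ECMO gives 5.1. Those are differences in event-free deaths, not shifts in the incidence odds ratio. The shares have no source, and Table 12 gives whole-trial Day 7 mortality, whereas most of these at-risk sets leave out the sickest subjects and run to Day 28. The 4.3% is the high-titer figure for an effect detectable with 80% power, not a forecast.

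**Sections 10.4 and 10.5 treat different kinds of outcome.** A score cannot be measured after death, whereas whether a subject ever entered ICU is still a fact. So the different rules are not in themselves a contradiction. The reversed order for ECMO remains awkward.

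**A composite is a different estimand.** This stands against replacing the tests, because the protocol names incidence as the secondary parameter and exact logistic regression as the method. It does not stand against a required companion.

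**Conclusion.** The point holds as a minor one, for five secondary endpoints. As defined, the item b odds ratio leans towards the arm with more deaths, and note ii commits to nothing that would show by how much. The lean is about 0.1 to 1.6 points (odds ratio 1.03 to 1.07) if death and event are independent, and up to 5.7 points at 10% v 4.3% only if every death pre-empts an event. These figures assume event risks of 5% to 40%, equal in both arms, and death rates applied to at-risk subsets for which the documents give no mortality. Against the precision of such small sets the independent-case shift is slight.

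The effect is probably smallest for new oxygen, where death without any oxygen should be rare, and larger for ventilation, ECMO and ARDS. The primary endpoint ranks death worst and mortality is tested separately, so neither is touched.

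**What to change.** Keep the protocol's incidence endpoints and exact logistic regression as they are. In SAP 10.4:

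- State in item b that a subject who dies without the event stays in the denominator as a non-event.
- Replace the optional wording on deaths in note ii with a required, pre-specified companion analysis for each incidence endpoint: new intervention (or new ARDS) or death through Day 28, with the same denominator and method, reported beside the incidence row.
- Show the number of deaths without the event, by arm, for each endpoint.

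This follows the precedent of 10.2b and needs no new data. The cost is five extra comparisons and one more table row per endpoint. For ECMO the composite will largely reflect mortality, and the table should say so.
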